7.2 Adverse Event Reporting

Adverse events will be graded according to CTCAE v4.03. This is an off-label indication for plerixafor. Investigators will reference safety information to assess expectedness: IB. All adverse events except those clearly attributable to the underlying disease will be reported, including definitely, probably and possibly related. Both Serious and Non-Serious Adverse Events will be clearly noted in source documentation and listed on study specific Case Report Forms (CRFs). The Protocol Director (PD) or designee will assess each Adverse Event (AE) to determine whether it is unexpected according to the Informed Consent, Protocol Document, or Investigator's Brochure, and related to the investigation. All Serious Adverse Events (SAEs) will be tracked until resolution, or until 30 after the last dose of the study treatment.

SAEs CTCAE Grade 3 and above, and all subsequent follow-up reports will be reported to the Stanford Cancer Institute Data and Safety Monitoring Committee (DSMC) using the study specific CRF regardless of the event's relatedness to the investigation. Following review by the DSMC, events meeting the IRB definition of 'Unanticipated Problem' will be reported to the IRB using eProtocol within 10 working days of DSMC review, or within 5 working days for deaths or life-threatening experiences.

In addition, within 24 hours (US) or one business day (EU) of first knowledge of such serious
and related adverse event, we will notify Sanofi via fax, attention Sanofi Pharmacovigilance
(PV), or via email at:
Additionally, the Investigator will transmit to Sanofi PV an information copy of
any such report sent to the governing regulatory authority, prior to or at the time of authority
filing. The Investigator will make available to Sanofi promptly such records as may be necessary
and pertinent to investigate any such expedited adverse event, if specifically requested by Sanofi

Furthermore, the Investigator will inform Sanofi of the following:

- Any events that result in protocol amendments for safety reasons, as well as any safety related regulatory action such as a clinical hold of the Research;
- Any pregnancies occurring in patients who are exposed to the Product in connection with the Research. Please see section 10.2.1.3 for additional reporting guidance;
- In addition, the Investigator will notify Sanofi within 24 hours (US) or one business day (EU) of first knowledge of any Product complaints (communication of dissatisfaction that alleges deficiencies related to the identity, quality, durability, effectiveness, safety, labeling, purity, stability, and appearance) by fax to Customer Services Europe,
- The Investigator will also inform Sanofi within 1 business day of becoming aware of any actions from any authority that may affect the performance of the Research

Safety reporting rules are to be complied with, according to current PV specifications (QGSD-007589). Sponsor is to provide Sanofi with: results relevant to final diagnosis of any SAE; routine transmission of any overdose with plerixafor; periodic reports; study report must contain section with safety review and conclusion –to be reviewed by Sanofi before finalization.

Pregnancy reporting

All patients must agree to an effective method of contraception while on study treatment and for at least 3 months following Plerixafor treatment (including both female patients of child-bearing potential and male patients with partners of child-bearing potential). Effective birth control includes: a) birth control pills, depot progesterone, or an intrauterine device plus one barrier method, or b) two barrier methods. Effective barrier methods are: male and female condoms, diaphragms, and spermicides (creams or gels that contain a chemical to kill sperm). For patients using a hormonal contraceptive method, information about any interaction of Plerixafor with hormonal contraceptives is not known.

The Investigator will inform Sanofi PV within 24 hours of the Investigator's first knowledge of pregnancy in a female patient or the female partner of a male patient at any time after the first dose of Plerixafor. Pregnant female patient(s) must not receive additional study treatment. The pregnancy will be followed until the outcome is known (i.e., delivery, elective termination, spontaneous abortion). The Investigator will obtain follow-up information no later than two months after the gestational period to obtain maternal, fetal, and neonatal outcome and any other relevant information. If the pregnancy results in the birth of a child, additional follow-up information may be requested. The Investigator must complete as much information as possible on the relevant Pregnancy Notification Forms (PNF) A and B, and fax the forms to the Genzyme PV.

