Another study is aiming to establish the maximum tolerated dose (MTD) of Plerixafor in combination with bortezomib in patients who have active relapse/refractory MM [69]. Patients with active disease received Plerixafor at the recommended dose SC on days 1-6 of every cycle. Planned dose levels include 160, 240, 320, 400, and 480 µg/kg. Bortezomib was given at the recommended dose twice a week on days 3, 6, 10, and 13 every 21 days. Dose levels include 1.0 and 1.3 mg/m2, 60-90 minutes after Plerixafor. Patients who had response or stable disease went on to receive a total of 8 cycles without planned maintenance therapy. The median number of cycles on therapy was 3 (1–11). Dose limiting toxicities including insomnia, restlessness, and psychosis were observed in two patients at dose level 6 (Plerixafor 400 µg/kg and bortezomib 1.3 mg/m²). To further explore the safety of maximum tolerated dose, three additional patients were enrolled at dose level 5b (Plerixafor 320 μg/kg and bortezomib 1.3 mg/m²). Overall, the combination proved to be well tolerated. There were no grade 4 toxicities. Grade 3 toxicities included lymphopenia (40%), hypophosphatemia (20%), anemia (10%), hyponatremia (10%), hypercalcemia (10%), and bone fracture due to myeloma bone disease (10%). One patient came off treatment due to grade 2 painful neuropathy at cycle 5. Twenty-three patients were evaluable for response, including 1 (4%) complete response (CR), 1 (4%) very good partial response (VGPR) and 3 (13%) MR, with an overall response rate (including MR) of 5 (22%) in this relapsed and refractory population. In addition, 15 (65%) patients achieved stable disease (SD), with just 3 (13%) having progressive disease (PD) as their best response. The combination of Plerixafor and bortezomib is generally well tolerated with minimal neuropathy or other toxicities seen to date. The responses observed are encouraging in this relapsed and refractory population. Plerixafor was able promote transient de-adhesion of MM cells and accessory cells in vivo in most of the patients, indicating that chemosensitization can potentially be achieved in patients with MM using this approach.

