Revascularization at sites of hypoxia results from the recruitment and stimulation of CXCR4-positive bone marrow-derived progenitor cells through local upregulation of SDF1- α , which is in turn under positive regulation by HIF-1 α [11, 72]. Of relevance, the process of vasculogenesis initiated after radiation therapy in an intracranial xenograft model of glioblastoma was recently shown to be a potential mechanism for disease recurrence [10]. In this model, Plerixafor was given chronically over a period that slightly overlapped with and extended beyond radiotherapy until hypoxia-induced SDF-1 α levels resolved to baseline. In treated animals, disease recurrence was prevented, likely due to the mitigating effect of Plerixafor on the influx of bone marrow-derived cells to the brain. Effective abrogation of revascularization through CXCR4 antagonism was also recently demonstrated in xenograft models of lung and breast, overcoming both the concomitant stimulation of angiogenesis by paclitaxel and G-CSF [73]. Taken together, these observations suggest a potential role for Plerixafor in directly sensitizing gliomas, and perhaps other solid cancers, to therapy or promote tumor cell apoptosis through deprivation of essential new vasculature.

Dose Selection in Combination with Chemotherapy

In preclinical animal toxicology studies, DLTs were primarily adverse neurologic events, including severe dyspnea, tremors, ventral recumbency, which, at higher dosages, progressed to convulsions. The MTD for these effects was approximately 70 mg/m², which correlates with a dose of approximately 1800 μ g/kg in humans. Early evidence of adverse neurologic effects, including diarrhea, muscle twitches, tremor, and tachycardia, were seen at doses of 17.5 to 35 mg/m². This is thought to scale to an approximate human equivalent dose of 470 to 940 μ g/kg. The effects tended to resolve within hours of the dose and appeared to be related to Cmax.

Plerixafor has been given at doses of up to 480 μg/kg SC and IV in healthy volunteers and in cancer patients. A maximum tolerated dose has not been established. Higher doses of Plerixafor injection were evaluated in healthy volunteers in three cohorts of six subjects who each received two different doses of Plerixafor separated by at least 2 weeks to allow for adequate pharmacodynamic wash-out [32]. The dosing cohorts evaluated were: 240 and 320 μg/kg (cohort 1); 320 and 400 μg/kg; (cohort 2); and 400 and 480 μg/kg (cohort 3). Plerixafor

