6.1 Dose Limiting Toxicities

DLT is defined as any hematologic or non-hematologic AE grade ≥3 with a suspected causal relationship to Plerixafor (including including ECG changes indicative of ischemia, ventricular tachycardia).

- Patients will be monitored for DLTs for 5 weeks from the start of the Plerixafor infusion.
- DLT's in the first cohort may occur before or after 14 days. If a DLT occurs in weeks 3 or 4 of treatment, we will treat next patient with a dose of 200 μg/kg/d x2 weeks. If a DLT occurs from the start of treatment through the second week of treatment, we will

Version #11, Date: 04-29-2015 Page 27 of 52

treat next patients at a dose of 100 μ g/kg/d x 4 weeks. If a patient experiences a DLT, the infusion will be discontinued. The next patient treated at the lower dose level as dictated by the mTPI table. If an early dose limiting toxicity occurs at lowest dose level (200 μ g/kg/d x 2 wk or 100 μ g/kg x 4wks) then the protocol will be stopped at that point.

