7. ADVERSE EVENTS AND REPORTING PROCEDURES

7.1 Potential Adverse Events

Safety will be assessed by monitoring clinical and laboratory evaluations and AEs.

Definitions

Adverse Event

An AE is any untoward medical occurrence associated with the use of the investigational product (active or placebo drug, biologic, or device) in a clinical investigation patient, which does not necessarily have a causal relationship with the investigational product. An AE can, therefore, be any unfavorable and unintended symptom, sign, disease or condition, or test abnormality whether or not considered related to the investigational product.

AEs may include, but are not limited to:

Subjective or objective symptoms spontaneously offered by the patient and/or observed by the investigator or medical staff

Clinically significant laboratory abnormalities

A significant worsening of the patient's condition from study entry

Disease signs and symptoms and/or laboratory abnormalities existing prior to the use of the study treatment that resolve but then recur after treatment

Disease signs and symptoms and/or laboratory abnormalities existing prior to the use of the study treatment which increase in frequency, intensity, or a change in quality after treatment

Version #11, Date: 04-29-2015 Page 28 of 52

Since prior studies using this medication have included premature ventricular contractions (PVCs), there will be a temporary interruption of plerixafor treatment for abnormalities in serum magnesium, calcium, or potassium at a Grade 2 or more severe. The study medication may be resumed following correction of these electrolyte abnormalities as confirmed by repeat serum level testing. Supplementation to include magnesium sulfate, calcium carbonate, or potassium chloride may be used as clinically indicated.

Serious Adverse Events (SAEs)

A SAE is any adverse event that results in any of the following outcomes:

- Death
- A life-threatening experience
- Requires inpatient hospitalization or prolongs existing hospitalization
- A persistent or significant disability/incapacity
- A congenital anomaly/birth defect
- Important medical events that may jeopardize the patient and may require medical or surgical intervention to prevent 1 of the outcomes listed above

Hospitalizations that occur under the following circumstances are not considered to be SAEs:

- were planned before entry into the clinical study;

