12.2 Interim analyses

Patient characteristics will be summarized using proportions for categorical variables, means and standard deviations for continuous variables (median and inter-quartile rages for variables that exhibit skewness). Adverse events and qualifying DLT will be tabulated by cohort, site and severity. Proportions of these patients in each response category will be tabulated; the combined proportion in categories CR, CRi, PR, SD will be computed along with an exact 95% confidence interval. Duration of response progression-free survival and overall survival will be computed from start of induction therapy and summarized with Kaplan-Meier estimates.

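### Section 7.2 excepts adverse events put down to the tumour from reporting, so non-serious events and SAEs below grade 3 that resemble glioblastoma symptoms can be missing from the adverse event table

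*Combined protocol and SAP*

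**What the plan says.** Section 7.1 defines an adverse event broadly, "whether or not considered related to the investigational product". Section 7.2 then narrows what is reported: "All adverse events except those clearly attributable to the underlying disease will be reported, including definitely, probably and possibly related". The sentence on recording that follows has no such limit: "Both Serious and Non-Serious Adverse Events will be clearly noted in source documentation and listed on study specific Case Report Forms (CRFs". A separate route sends SAEs of grade 3 and above to the DSMC "using the study specific CRF regardless of the event's relatedness to the investigation".

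The adverse event table is planned in section 12.2: "Adverse events and qualifying DLT will be tabulated by cohort, site and severity". Section 1.1 makes safety a primary objective, and section 2.4 describes an open, single-group trial.

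The background (section 2.5) names neurologic and psychiatric effects of the drug. In animals, "DLTs were primarily adverse neurologic events, including severe dyspnea, tremors, ventral recumbency, which, at higher dosages, progressed to convulsions". In the myeloma combination trial, "Dose limiting toxicities including insomnia, restlessness, and psychosis were observed in two patients at dose level 6", that level being plerixafor 400 µg/kg with bortezomib. Section 7.1 adds a panic attack with paresthesias as one of four SAEs in the 10-day infusion study.

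**The concern.** Tremor, seizure, insomnia, restlessness, headache and dizziness appear in the protocol as plerixafor effects, in animals or in patients. Each can also plausibly be a symptom of a brain tumour. A rule that excepts tumour-attributed events therefore acts on part of the signal that the trial should be looking for. With no control arm, an excess cannot be recognised by comparison. What remains is the pattern within and across patients, above all the timing of onset against the infusion. Section 2.5 says that the early neurologic effects in animals tended to resolve within hours and seemed tied to peak concentration, so timing is informative. An event that is never entered has no onset date to examine later.

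**Working it through.** **1. What happens to an event judged plainly due to tumour.** Applying the sentences of 7.2 in turn:

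| Event | Main reporting sentence | DSMC route | Result |
|---|---|---|---|
| SAE, grade 3 or higher | excepted | reported, any attribution | kept |
| SAE, below grade 3 | excepted | not covered | rests on the CRF-listing sentence |
| Non-serious, grade 3 or higher | excepted | not covered | rests on the CRF-listing sentence |
| Non-serious, grade 1 or 2 | excepted | not covered | rests on the CRF-listing sentence |

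For the last three rows there are two readings. If the CRF sentence covers all events, it sits uneasily with the sentence before it. If it covers only reportable events, these rows are lost to the table in 12.2. The text does not choose. Nor does the relatedness scale in 7.1 help: it runs from definite and possible to unlikely and unrelated, has no disease category, and lacks the probable category that 7.2 uses.

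**2. Size in the adverse event table.** Let T be the proportion of patients with a given event and f the share of those patients whose event is excepted. The tabulated proportion is R = T × (1 − f), so R cannot exceed T. The documents give neither T nor f, so R − T cannot be computed. What follows from the sample sizes is the step for each patient whose only such event is left out:
- all patients: 1/29 = 3.4 percentage points
- Phase II: 1/20 = 5.0 points
- Phase I: 1/9 = 11.1 points

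**3. Does 7.2 change the dose decisions?** Table 12.1 gives, for three patients at a dose, 0 DLTs = E, 1 = S, 2 = D. One event more or less therefore changes the action. The question is which section removes it.
- Section 6.1: "DLT is defined as any hematologic or non-hematologic AE grade ≥3 with a suspected causal relationship to Plerixafor". Section 4.2 carries the same condition. An event judged plainly due to tumour fails it whether or not 7.2 reports the event.
- Section 10.1.2 refers to cardiac arrhythmia or grade III or IV events with no causality condition, and words the outcome as an absence. Under that text, a non-serious grade 3 or 4 event left out through 7.2 would go uncounted.

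Illustration of misattribution under 6.1, with a true DLT rate at the 30% target and an assumed share m (0 to 50%, not from the documents) of true DLTs put down to tumour. Observed rate q = 0.30 × (1 − m); chance of no DLT in three patients = (1 − q)³.
- m = 0: q = 0.30; 0.70³ = 34%
- m = 10%: q = 0.27; 0.73³ = 39%
- m = 30%: q = 0.21; 0.79³ = 49%
- m = 50%: q = 0.15; 0.85³ = 61%

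This loss comes from the causality condition in 6.1. It would be the same with the exception in 7.2 deleted.

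**The case against.** The case against is substantial. The exception covers only plain tumour events, so doubtful ones stay reportable. The CRF sentence carries no attribution limit, section 4 follows adverse events to 30 days after the infusion without one, and 7.2 tracks all SAEs. The Protocol Director or a designee assesses each event, and the DSMC may audit source documents and CRFs. The toxicity profile is not mainly neurologic: three of the four SAEs in the infusion study were thrombocytopenia, line infection and arrhythmia, section 2.5 reports cardiac toxicity, and the psychosis and restlessness arose in combination with bortezomib. If the tumour attributions are right, no drug toxicity is missed. Without a control arm, a table of all events cannot by itself separate drug from tumour.

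Much of this stands, and it limits the point. It does not remove it. No criterion is given for what counts as a plain tumour event, and the wider sentences do not say that excepted events enter the table. An all-events table cannot prove causation, but it preserves the onset data on which any later assessment depends.

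A reader might go further and infer that 7.2 biases the DLT endpoint downward and moves Table 12.1 from S to E. Under section 6.1 it does not, as shown above. Nor do the documents support saying that such events leave no record at all, or that the treating investigator decides alone.

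**Conclusion.** The point holds in a limited form. Section 7.2 is narrower than the definition in 7.1 and is not squared with its own recording sentence. If the exception is applied at CRF entry, non-serious events of any grade and SAEs below grade 3 judged tumour-related are missing from the 12.2 table, which then understates events as 7.1 defines them. The direction is certain on that reading; the amount is unknown. SAEs of grade 3 and above are safe through the DSMC route. The DLT count is touched only if section 10.1.2, rather than 6.1, is the operative definition. The conclusion rests on the restrictive reading of 7.2 and on the overlap between the named drug effects and tumour symptoms, which is plausible but not quantified in the documents.

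**What to change.** In 7.2, delete the exception for CRF capture. Record every adverse event from Day 1 to 30 days after the infusion, with grade, onset relative to infusion start and end, and attribution as a separate field that includes a disease category. Align the attribution terms in 7.1 and 7.2. In 12.2, tabulate nervous-system and psychiatric events both regardless of attribution and by attribution. Causality filters for expedited reporting can stay. Separately, reconcile the DLT definitions in 6.1 and 10.1.2 so that one text governs Table 12.1.

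The cost is a wording change and some extra CRF entries in 29 patients. The tables will contain more tumour symptoms, which the split by attribution makes readable.

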8. CORRELATIVE/SPECIAL STUDIES

Patients will undergo pharmacokinetic analysis

8.1 Laboratory Correlative Studies

8.1.1 Pharmacokinetic analysis of Plerixafor

8.1.1.1 Collection of Specimen(s)

Pharmacokinetics

Patients enrolled in the Phase I will undergo pharmacokinetic analysis. 2.5 mL of blood will be collected in Na-Heparin tubes. Samples will be drawn prior to and 1 hour after start of the infusion of Plerixafor and weekly afterwards while infusions continue, the last sample being drawn at the time the infusion is discontinued. Samples will be processed at Stanford and then sent to Tandem Laboratories who will measure plasma levels of Plerixafor.

SDF-1

Blood samples will be collected in two 8 mL green top tubes at within 24 hours to the start of Plerixafor infusion and at time of infusion discontinuation (+/- 1 week)

8.1.1.2 Handling of Specimens(s)

Version #11, Date: 04-29-2015 CONFIDENTIAL

Pharmacokinetics:

Minimum of 0.5 mL in the primary and 0.5 mL in the back up

SDF-1

- 1. Peripheral blood will be drawn into 2 green top tubes and placed immediately on ice.
- 2. Peripheral blood mononuclear cells will be isolated by Ficoll centrifugation technique under sterile conditions:
- 3. 2 green top tubes (16 mL) will be placed into one 50mL conical tube
- 4. Volume will be brought to 50mL with RPMI per conical.
- 5. One 50mL sample will be divided into two 50mL tubes and underlayed with 13mL of Ficoll (now total of 2 conicals).
- 6. Centrifuge at 400G for 30min with NO break at room temperature (24C).
- 7. Plasma layer will be removed and frozen in four aliquots at -80C for future assessment of SDF-1 level by ELISA.
- 8. Buffycoat will be removed and washed 3 times with 30mL of RPMI in a 50mL tube pelleting by centrifuge for 15 minutes at 1200G (1800 RPM) with break.
- 9. Sample will be resuspended in 1mL of cRPMI and cell count performed.
- 10. Aliquots of live cells ($20x10^6$ per aliquot) will be frozen in FCS + 10% DMSO. Samples will be placed in -80 for 3 days then in liquid nitrogen for storage

8.1.1.3 Shipping of Specimen(s)

PKs will be batch shipped to Tandem Laboratories at the completion of the Phase I.

SDF-1 will be picked up by a representative of lab at Stanford University

